9.9.1.2 Definition of Evaluability

All randomised subjects who receive at least one dose of placebo or TD139 will be included in the safety analysis.

All randomised subjects who receive all doses of TD139, have sufficient plasma concentration by time profiles and who do not violate the protocol in such a way that may

Clinical Study Protocol Version: FINAL 6.0 / 05 April 2016 Confidential Page 61 of 73

invalidate or bias the results (major protocol violators) will be included in the pharmacokinetic analysis.

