There will be an interim review after Cohort 1 has been dosed to review the available data. Following a review of this data, if it is decided that it meets the dose escalation requirements then Cohort 2 (8 subjects, 5 TD139 and 3 placebo) will receive the next dose level. An interim review would then take place after Cohort 2 has been dose to review the available data. Following a review of this data, if it is decided that it meets the dose escalation requirements then Cohort 3 (8 subjects, 5 TD139 and 3 placebo) will receive a third dose level (Outcome 1). If it is decided that the data in Cohort 2 does not meet the dose escalation requirements, a 4 further subjects would be dosed in Cohort 2 with the same dose level (3 TD139 and 1 placebo) (Outcome 2).

After the interim review of Cohort 1 data, if it is decided that the dose escalation requirements have not been met, 4 further subjects would be dosed in Cohort 1 with 3mg (3 TD139 and 1 placebo). After the extra subjects have been dosed an interim review would then take place to review the data, before moving on to the next dose level in Cohort 2 (8

Clinical Study Protocol

RD 676/25641 Version: FINAL 6.0 / 05 April 2016 Page 27 of 73

subjects, 5 TD139 and 3 placebo). An interim review would then take place after Cohort 2 has been completed to review the available data. Following a review of this data, if it is decided that it meets the dose escalation requirements then no further subjects would be dosed (Outcome 3). If it is decided that the data in Cohort 2 does not meet the dose escalation requirements, a 4 further subjects would be dosed in Cohort 2 with the same dose level (3 TD139 and 1 placebo) (Outcome 4).

The highest acceptable dose level in Part 1 of the study will not be exceeded in Part 2. Part 2 will be discontinued at any time if any unacceptable safety findings are identified (see Study Stopping Criteria). At the interim review meetings it may be decided it is not appropriate to escalate the dose. In this event the same dose, an intermediate dose or a lower dose may be given following discussion between the Sponsor and the Chief/Principal Investigators. The dose and PK sampling times may also be modified following a review of the data.

Part 1

Pre-study assessments

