Each subject will receive either a single dose of TD139 or placebo via DPI once daily for 14 days, following an overnight fast on day-1. The randomisation code will be generated using the PROC PLAN procedure of SAS®. Subjects will remain in the unit until 12 hrs post-dose on Day 1, providing the scheduled assessments have been completed and there are no ongoing safety concerns. Subjects will then return to the Clinical Centre on Days 2, 3, 7, 14 and 15 for scheduled assessments and to receive the IMP. On Days when subjects are not required to attend the Clinical Centre, they will self administer the IMP at home.

During the Study Period, assessments will include:

- Vital signs (supine blood pressure, pulse, O₂ saturation, oral temperature and respiratory rate)
- Lung function testing
- 12-lead ECG
- Physical examination
- Laboratory safety screen (haematology, biochemistry, urinalysis and urine drugs of abuse screen)
- Blood samples for PK, PG and PD measurements
- BAL fluid sampling for PK, PG and PD measurements.
- Exhaled breath condensate (EBC) collection for PD measurements

All Adverse Events (AE) and concomitant medications will be recorded from the time of the screening visit until the post-study follow-up visit.

Post-study assessments will be carried out 26 - 30 days after the last day of the Study Period (See Table 9.7.1).

The conclusion of the study is defined as the last visit of the last subject.

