9.4.3 Removal of Subjects from Therapy or Assessment

Each subject will be informed of their right to withdraw from the study at any time and for any reason.

The Investigator may withdraw a subject from the study at any time for any of the following reasons:

- If a subject experiences a serious or intolerable AE, that prevents them from continuing. As there have been no significant clinical or pre-clinical toxicology flags in studies with TD139 there are no drug specific side effects anticipated.
- If a subject incurs a significant protocol violation.

• At the request of the Sponsor.

- If the Investigator considers that remaining in the study compromises the subject's health or the subject is not sufficiently cooperative.
- If a subject is lost to follow-up.

The reasons for any subject withdrawal will be recorded on the study completion form of the Case Report Form (CRF).

If a subject is withdrawn, chooses to withdraw from the study for any reason or prematurely discontinues the IMP, the Chief Investigator will make every possible effort to perform the evaluations described for the Post Study Visit. At the discretion of the Chief Investigator, the subject could continue with study assessments after discontinuation of IMP until the Post-Study Visit is performed. Once a subject prematurely discontinues the IMP or is withdrawn the subject cannot re-enter the study. The data collected from withdrawn subjects will be included in the study report.

In the event of any abnormalities considered to be clinically significant by the investigating physician, subjects will be followed up with appropriate medical management until values are considered to be clinically acceptable. Referral or collaborative care will be organized if considered necessary.

In **Part 1** up to 36 subjects and in **Part 2** up to 24 subjects are required to complete the study. Subjects who withdraw from the study before receiving any study medication will be replaced. Subjects who are withdrawn from the study due to significant drug-related AEs will not be replaced. Replacement of all other subjects withdrawn from the study after receiving study medication will be decided on a case by case basis by the Chief Investigator and Sponsor.

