9.6.7 Selection of Doses in the Study

For Part 1, the planned doses of TD139 to be studied are: 0.15mg, 1.5mg, 3mg, 10mg, 20mg and 50mg. The maximum dose of TD139 (50 mg) will not be exceeded.

The planned dose levels have been selected following review of non-clinical pharmacokinetic, safety pharmacology and toxicology data.

Pharmacokinetic, toxicokinetic and toxicology studies in mice, rats and dogs indicate the drug is readily bioavailable via the inhaled route with little or no accumulation after 14-day dosing and is excreted in the faeces with a $t_{1/2}$ of approximately 6 h. The human starting dose is 0.15mg. Given the NOAEL's in mouse and dog studies, this FIM dose is over 100-fold below the industry accepted safe starting dose. Given the lack of adverse effects seen in the two species, no direct anticipated adverse drug specific side effects are expected in man nor are any drug interactions anticipated given the clear cytochrome profiling. Further details regarding non-clinical pharmacokinetic, safety pharmacology and toxicology data can be found in the IB^[11].

GB-HV-01 Clinical Study Protocol Confidential RD 676/25641 Version: FINAL 6.0 / 05 April 2016 Page 44 of 73

If unacceptable safety findings are identified or if there is any indication that it is not possible to maintain an ample safety margin with higher doses in subsequent cohorts the dose escalation will be stopped or modified accordingly. Subsequent doses therefore may vary from those planned depending on safety and pharmacokinetic results. If the dose escalation stopping criteria for Part 1 in section 9.2.3 are met, then the dose level that was tested will not be repeated or exceeded, however a lower dose may be given following discussion between the Sponsor and the Investigator.

The selection of the 3mg starting dose for **Part 2** was determined based upon interim safety and PK data from **Part 1** (in single doses up to 10mg) and on pre-clinical efficacy and safety data. The highest acceptable dose level in Part 1 of the study will not be exceeded in Part 2.

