- 7. Spirometry to be performed on Day 14 **prior** to BAL sampling procedure.
- 8. Subjects will be dosed with the IMP at the Clinical Centre during clinic visits and will self administer the IMP on non clinic visit days.
- 9. PK blood sampling will be taken on Day 1 prior to dosing = 0h and then at 15min, 30min, 45min, 1h, 2h, 3h, 4h, 5h, 6h and 12h post-dose; Day 2, 3 and 7 prior to dosing = 0h; Day 14 prior to dosing = 0h and then at 15min, 30min, 45min, 1h, 2h, 3h, 4h, 5h, 6h, 12h and 24h post-dose.
- 10. Blood sampling for pharmacogenetic analysis (mRNA) and peripheral blood flow cytometry will be taken Day 1 prior to dosing = 0h and then at 30 min post-dose, Day 7 at 2h post-dose and Day 14 prior to dosing = 0h and then at 30 min post-dose.
- 11. Blood sampling for pharmacogenetic analysis of peripheral blood mononuclear cells (PBMCs) will be taken Day 1 prior to dosing = 0h and Day 14 at 30 min post-dose.
- 12. Blood sampling for Galectin-3 analysis will be taken on Day 1 prior to dosing = 0h and then at 5h post-dose, Day 7 (anytime) and Day 14 prior to dosing = 0h.
- 13. Exhaled Breath Condensate to be performed on Day 14 between 1h and 2h post-dose.
- 14. BAL to be performed on Day 14 between 1h and 4h post-dose. (It is essential post treatment bronchoscopy is performed in the morning.)

GB-HV-01 Clinical Study Protocol Confidential RD 676/25641 Version: FINAL 6.0 / 05 April 2016 Page 51 of 73

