The same analysis will be carried out (for C_{max} , AUC_{τ} , $t\frac{1}{2}$ and CL/F) for Part 2 of the study on Days 1, 7 and 14.

GB-HV-01 Clinical Study Protocol Confidential RD 676/25641 Version: FINAL 6.0 / 05 April 2016 Page 62 of 73

Accumulation Assessment: Log-transformed trough levels at pre-dose on Day 2 through to Day 14 will be used to establish any accumulation of TD139. The ratio of trough concentrations on each consecutive day will be presented and summarized along with a 90% confidence interval. The analysis will be done for each dose level.

Assessment of Steady State: Log-transformed trough concentration levels at pre-dose on Days 7, and 14 will be subjected to mixed effects ANOVA with study day as a fixed effect and subject as a random effect in order to establish whether and when steady state has been attained for each dose level. Back-transformed ratios for the Day 14/Day 7, comparisons will be presented along with corresponding 90% CI.

Additional PK Assessments:

Alveolar macrophage and BAL fluid concentrations of TD139 will be presented as a data listing.

Drug compartment measurements in BAL and alveolar macrophages will be analysed as per the method set out in the study by Naderer *et al*^[1] (e.g. TD139AM = TD139pellet/VAC [where the volume of alveolar cells - VAC, is estimated at 2.42μ l/106 cells])^[1].

PD Assessments:

Macrophage morphology parameters (*ex-vivo* macrophage function and BAL soluble markers) will be presented as a data listing.

Exhaled breath condensate data will be presented as a data listing.

Descriptive statistics of absolute and change from baseline for peripheral blood flow cytometry data will be presented at each time point by dose.

Descriptive statistics of absolute and change from baseline for Galectin-3 plasma concentration data will be presented at each time point by dose.

PG Assessments:

Macrophage phenotypic, mRNA pattern expression analysis from BAL and analysis of peripheral blood mononuclear cells for IPF gene signatures will be presented as a data listing.

Descriptive statistics of absolute and change from baseline of mRNA expression levels from blood leucocytes will be presented at each time point by dose.

Safety Assessments:

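### The PK analysis set requires every dose of TD139, so in Part 2 one missed home dose discards a valid Day 1 profile and valid Day 2 and Day 3 troughs

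*Protocol*

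**What the plan says.** Section 9.9.1.2 contains the protocol's only definition of the PK set: "All randomised subjects who receive all doses of TD139, have sufficient plasma concentration by time profiles", and no violation that could invalidate or bias the results. The dosing condition stands beside the condition on profiles, so a complete profile does not by itself keep a subject in. The text makes no distinction between Part 1 and Part 2, between days or between analyses. The safety set in the same section needs only one dose.

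Section 9.9.1.3 analyses Part 2 PK by day: the dose-proportionality and dose-independence analyses are repeated "for Part 2 of the study on Days 1, 7 and 14". Accumulation is assessed per dose level from the pre-dose samples, starting on Day 2: "The ratio of trough concentrations on each consecutive day will be presented and summarized along with a 90% confidence interval".

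Part 2 dosing is once daily for 14 days. Under Table 9.7.2 footnote 8, subjects are dosed at the centre at clinic visits and "will self administer the IMP on non clinic visit days". Section 9.1 has subjects return "on Days 2, 3, 7, 14 and 15 for scheduled assessments and to receive the IMP".

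On withdrawals, section 9.4.3 says: "The data collected from withdrawn subjects will be included in the study report".

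**The concern.** The rule was written as if PK evaluability were a property of the whole course. That fits a single-dose part. It does not fit a 14-day course whose PK is analysed day by day and whose early samples are complete before any unsupervised dose is taken.

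A dose missed on Day 4 or later, or a stop after Day 3, comes after the Day 1 profile and the Day 2 and Day 3 troughs have been collected. It cannot change them, whatever the half-life. Excluding them therefore has no pharmacokinetic reason, and it wastes data from a cohort of five.

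The loss is not always random. Subjects who stop early because of an adverse event fall out of the set. So does anyone whose treatment code is broken before Day 14, because section 9.6.9 then requires withdrawal. Under section 9.4.3, subjects withdrawn for significant drug-related adverse events are not replaced. If tolerability is related to exposure, the exposure summaries would be selective. The protocol does not establish that it is related, or in which direction.

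The term itself is also unclear. Section 9.1 lists Day 15 among the visits at which subjects receive the product, against 14 days of dosing. A test based on all doses needs a single count.

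**Working it through.** The protocol gives no figure to reproduce: section 9.9.2 states that no formal sample size calculation was made.

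**1. Home doses.** Clinic dosing days within the 14-day course are 1, 2, 3, 7 and 14 (section 9.1, Table 9.7.2). Home doses are Days 4, 5, 6 (three) and Days 8-13 (six): 3 + 6 = 9.

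**2. Which samples come first.** Table 9.7.2 footnote 9 takes the Day 1 profile from pre-dose to 12 h, and pre-dose samples on Days 2, 3, 7 and 14. The first home dose is on Day 4, so the Day 1 profile and the Day 2 and Day 3 troughs precede all nine. Days 2 and 3 are also the only adjacent study days with a trough on each, so the one true consecutive-day ratio in the accumulation assessment uses only samples that no home dose can affect.

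**3. Active subjects per dose level.** 5 in a cohort of 8. With the expansion ("4 further subjects would be dosed in Cohort 1 with 3mg (3 TD139 and 1 placebo") this becomes 5 + 3 = 8.

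**4. Chance of staying in the set.** Let p be the probability that a home dose is taken. The protocol gives no value, so p is an assumption. With independent misses a subject stays evaluable with probability q = p^9.

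| p (assumed) | q = p^9 | all 5 kept, q^5 | expected kept, 5q | all 8 kept, q^8 | expected kept, 8q |
|---|---|---|---|---|---|
| 0.99 | 0.914 | 0.636 | 4.57 | 0.485 | 7.31 |
| 0.98 | 0.834 | 0.403 | 4.17 | 0.233 | 6.67 |
| 0.95 | 0.630 | 0.099 | 3.15 | 0.025 | 5.04 |

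Misses that cluster in a few subjects cost less. Take a mean of 98% made up of 80% of subjects at 100% and 20% at 90%: q = 0.8 × 1 + 0.2 × 0.9^9 = 0.8 + 0.2 × 0.387 = 0.877, and all five are kept with probability 0.877^5 = 0.52.

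**5. Precision of a single-cohort mean.** The half-width of a 90% confidence interval on the log scale, in SD units, is t(0.95, n−1)/√n. This applies, for example, to the Day 3/Day 2 trough ratio.

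- n = 5: 2.132/√5 = 0.953
- n = 4: 2.353/√4 = 1.177, ratio 1.23 to n = 5
- n = 3: 2.920/√3 = 1.686, ratio 1.77 to n = 5
- n = 8: 1.895/√8 = 0.670; n = 7: 1.943/√7 = 0.734, ratio 1.10

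These ratios need no adherence assumption, only the same SD before and after.

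**6. Precision of the power-model slope.** The half-width of its 95% interval is proportional to t(0.975, N−2)/√Σ(x − x̄)², with x the log dose. The later Part 2 doses are not legible, so dose sets of 3/10/20, 3/10/50 and 3/5/10 mg were assumed, with five active subjects at each level. Losing one subject widens the interval by about 1% (middle dose) to 8% (an end dose). With two dose levels, allowing for expansion of either or both, the range is about 4% to 9%.

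**The case against.** The strongest reply is that the protocol says who will be included and never says that nobody else may be, and that section 9.9.1.3 leaves full analysis details to a statistical analysis plan that is not shown. The first part is true as grammar. But the sentence stands under a heading on evaluability and is the only definition of who enters the PK analysis. The second does not help: this is a rule the protocol has fixed, and a plan with day-by-day evaluability would depart from it. Section 9.4.3 keeps withdrawn subjects' data in the report, perhaps as listings, but does not return them to the analysis.

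Several points limit the size, and they stand:

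- The 23% and 77% figures are for the worst-hit analysis, a single-cohort mean of five. For the pooled slope the loss of one subject costs about 1-9%, and for an expanded cohort mean about 10%.
- The loss probabilities depend wholly on assumed adherence. The course is short, with a Day 7 clinic visit, a dosing diary and return of used and unused medication, so 95% with independent misses may be pessimistic.
- A stop before Day 3 loses samples that were never taken, which no definition can restore.
- PK is a secondary, estimation-only objective. Neither the interim review nor the Cmax/AUC stopping rule is shown to use this set.
- The Day 15 wording may only reflect the 24 h sample after the Day 14 dose. It is a side issue, relevant because the test counts doses.
- A fixed all-doses set keeps the same subjects across days, which suits the Day 14/Day 7 steady-state comparison. That is a reason to keep it as a sensitivity analysis, but not to apply it to Day 1.

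**Conclusion.** The point holds. In Part 2 the all-doses condition excludes Day 1 profiles and Day 2 and Day 3 troughs because of events that cannot have affected them, and no other section restores them to the analysis. Part 1 is unaffected, and so is the primary safety analysis.

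The consequence is mainly lost precision in cohorts of five. One subject lost costs 23% on the width of a single-cohort 90% interval, and two cost 77%. How often this happens cannot be known from the protocol. At assumed adherence of 95-99% per home dose, the chance that at least one of five is excluded runs from 90% down to 36% with independent misses, and is lower if misses cluster. Selection bias is possible after adverse-event stops but is not demonstrated. The rule should be changed. It does not threaten the trial's main conclusions.

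**What to change.** In section 9.9.1.2, define PK evaluability for Part 2 by profile or sampling day:

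1. Day 1 profile and Day 2 and Day 3 troughs: every subject who took the doses due before that sample.
2. Day 7 trough: every subject who took the doses within a pre-specified number of half-lives before it.
3. Day 14 profile: the same window, plus the Day 14 dose.

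Base the window on the human half-life from Part 1, not on the animal value in section 9.6.7 ("Pharmacokinetic, toxicokinetic and toxicology studies in mice, rats and dogs indicate the drug is readily bioavailable"). Flag earlier missed doses in the listings, and keep the all-doses set as a sensitivity analysis. Reconcile the Day 15 wording in section 9.1 with 14 days of dosing so that the dose count has one meaning.

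The cost is one paragraph in the protocol, carried into the statistical analysis plan, and one sensitivity table. The paragraph needs a written amendment under section 10.2. No new data are needed, since section 9.6.11 already records dosing times in the CRF and diary. The one drawback is that n may differ between days, so each table should show it.

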9.9.1.3 Description of Statistical Methods

Simbec Research Limited will carry out the statistical analysis. Full details of the statistical analyses of the data will be documented in an agreed statistical analysis plan, which will be finalised prior to locking the database and subsequent analysis of the study data.

The pharmacokinetic parameters of TD139 in plasma will be determined from the individual concentration versus time data using WinNonlin Phoenix 32. For the calculation of derived pharmacokinetic parameters, concentrations below the limit of quantification (BLQ) will be assigned a value of zero. In case of a deviation from the theoretical time, the actual time of blood sample will be used in the calculation of the derived pharmacokinetic parameters.

Derived pharmacokinetic parameters of TD139 in plasma will be listed and summarised for each treatment. The descriptive statistics presented will be N, n, arithmetic mean, arithmetic standard deviation (SD), coefficient of variation (CV%), minimum, median, maximum and geometric mean (with the exception of t_{max}). The results for t_{max} will be reverted back to the nominal time.

Mean and individual plasma concentration-time curves of TD139 in plasma will be presented for each dose on both linear and semi-logarithmic scales.

Statistical analysis will be performed using SAS® version 9.1.3 or higher.

Dose-Proportionality/Independence: Dose proportionality will be assessed by performing a regression analysis of the log-transformed C_{max} , AUC_{0-t} and AUC_{0-inf} values versus the log-transformed dose using the power model with a fixed effect for dose and a random effect for subject. For each parameter a point estimate and 95% confidence interval will be calculated for the slope of the regression line.

The power model is defined as:

$$log_e(C_{max}, AUC_{0-t}, AUC_{0-inf}) = \alpha + \beta log_e(Dose) + \varepsilon$$
,

where α is the intercept, β is the slope and ϵ is the error term.

Dose independence will be assessed for t½ and CL/F by performing a regression analysis of the untransformed parameters versus dose with a fixed effect for dose and a random effect for subject. For each parameter a point estimate and corresponding 95% confidence interval will be calculated for the slope of the regression line.

Derived pharmacokinetic parameters will be presented graphically for mean C_{max} , AUC_{0-t} , AUC_{0-inf} , $t^{1}/_{2}$ and CL/F versus dose.

The same analysis will be carried out (for C_{max} , AUC_{τ} , $t\frac{1}{2}$ and CL/F) for Part 2 of the study on Days 1, 7 and 14.

GB-HV-01 Clinical Study Protocol Confidential RD 676/25641 Version: FINAL 6.0 / 05 April 2016 Page 62 of 73

Accumulation Assessment: Log-transformed trough levels at pre-dose on Day 2 through to Day 14 will be used to establish any accumulation of TD139. The ratio of trough concentrations on each consecutive day will be presented and summarized along with a 90% confidence interval. The analysis will be done for each dose level.

Assessment of Steady State: Log-transformed trough concentration levels at pre-dose on Days 7, and 14 will be subjected to mixed effects ANOVA with study day as a fixed effect and subject as a random effect in order to establish whether and when steady state has been attained for each dose level. Back-transformed ratios for the Day 14/Day 7, comparisons will be presented along with corresponding 90% CI.

Additional PK Assessments:

Alveolar macrophage and BAL fluid concentrations of TD139 will be presented as a data listing.

Drug compartment measurements in BAL and alveolar macrophages will be analysed as per the method set out in the study by Naderer *et al*^[1] (e.g. TD139AM = TD139pellet/VAC [where the volume of alveolar cells - VAC, is estimated at 2.42μ l/106 cells])^[1].

PD Assessments:

Macrophage morphology parameters (*ex-vivo* macrophage function and BAL soluble markers) will be presented as a data listing.

Exhaled breath condensate data will be presented as a data listing.

Descriptive statistics of absolute and change from baseline for peripheral blood flow cytometry data will be presented at each time point by dose.

Descriptive statistics of absolute and change from baseline for Galectin-3 plasma concentration data will be presented at each time point by dose.

PG Assessments:

Macrophage phenotypic, mRNA pattern expression analysis from BAL and analysis of peripheral blood mononuclear cells for IPF gene signatures will be presented as a data listing.

Descriptive statistics of absolute and change from baseline of mRNA expression levels from blood leucocytes will be presented at each time point by dose.

Safety Assessments:

Vital signs parameters will be listed with any out of normal range values flagged. Descriptive statistics of absolute and change from baseline (pre-dose) supine systolic and diastolic blood pressure, supine pulse rate, respiration rate, oral temperature and O_2 saturation at each time point, up to and including Day 15, will be tabulated by dose.

The mean change from baseline data will also be plotted by dose across time, up to and including Day 15.

12-Lead ECG parameters will be listed with any out of normal range values flagged. Descriptive statistics of absolute and change from baseline (pre-dose) heart rate, PR interval, QRS interval, QT interval and QTcB interval at each time point, up to and including day 15, will be tabulated by dose.

Confidential Page 63 of 73

The mean change from baseline data will also be plotted by dose across time, up to and including Day 15.

In addition, frequencies of QTcB data will be calculated according to the following categories:

For absolute values

- OTcB > 450 mSec
- QTcB > 480 mSec
- QTcB > 500 mSec

For change from baseline

- QTcB increase > 30 mSec
- QTcB increase > 60 mSec

All adverse events will be coded using the MedDRA dictionary, version 16.1.

All adverse events, including those that occur prior to the first administration of the study drug, will be listed. Only treatment-emergent adverse events (TEAEs), i.e. existing conditions that worsen or events that occur during the course of the study after administration of study drug, will be included within the summary tables. Adverse event summaries will be presented by treatment and overall (data from all dose groups will be pooled).

An overall summary of adverse events will be produced including the number of TEAEs; the number and percentage of subjects reporting at least one: TEAE, serious TEAE, TEAE leading to withdrawal from the study; the number and percentage of subjects reporting TEAEs by severity and relationship to study drug.

The number of TEAEs and the number and percentage of subjects reporting at least one TEAE will be tabulated by system organ class (SOC) and preferred term (PT). A subject reporting multiple episodes of a particular adverse event within a study period will only contribute one count towards the corresponding system organ class and preferred term within that study period.

In addition, the number and percentage of subjects reporting TEAEs will be tabulated by maximum severity and strongest relationship to study drug. For the summary of TEAEs by severity, if a subject has multiple events occurring within the same SOC or preferred term, the event with the highest severity will be counted. Similarly, for TEAEs by relationship to study drug, if a subject has multiple events occurring within the same SOC or preferred term, the event with the highest association to study drug will be counted.

Biochemistry, haematology and urinalysis parameters will be listed with any out of normal range values flagged. Laboratory test results that are out of normal range will also be presented separately along with normal reference ranges. Descriptive statistics of absolute and change from baseline (pre-dose) values for each biochemistry and haematology parameter at each time point, up to and including day 15, will be tabulated by dose.

GB-HV-01 Clinical Study Protocol Confidential RD 676/25641 Version: FINAL 6.0 / 05 April 2016 Page 64 of 73

Frequencies of the total number of subjects randomised, completed, and prematurely discontinued (including reason for discontinuation) from the study will be summarised by dose. Additionally the frequency of subjects within each analysis population (safety, PK) will be summarised by dose.

Demographic data will be listed and descriptive statistics will be tabulated for the continuous variables age, height, weight and BMI and frequencies for the categorical variable race. These descriptive statistics will be presented by dose and overall.

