9.9 Statistical Methods and Determination of Sample Size

9.9.1 Statistical and Analytical Plan

9.9.1.1 Primary and Secondary Variables for Assessment

The primary safety assessment variables will be the vital signs data, ECG data, laboratory data and the adverse events reported.

The secondary pharmacokinetic variables will be the following non-compartmental pharmacokinetic end-points:

	Politica
• C _{max}	Maximum plasma concentration
• t _{max}	The time to maximum observed concentration sampled during
	a dosing interval
 λ_z 	Elimination rate constant
• t _{1/2}	Terminal half-life
• AUC _{0-t}	Area under the plasma concentration-time curve (AUC) from the
	time of dosing to the time of the last observed concentration
• AUC _{0-τ}	Area under the plasma concentration-time curve (AUC) from the
	time of dosing to time t at steady state
• AUC _{0-inf}	The area under the curve (AUC) extrapolated to infinity from dosing
	time, based on the last observed concentration
• CL/F	Plasma clearance, calculated as Dose / $AUC_{0\text{-}inf}$
AUC% extrapolated	Residual area

The secondary pharmacodynamic variables will be the peripheral blood flow cytometry data and galectin-3 plasma concentration data.

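### Part 2 PK parameters are to be analysed on Day 7, when only a pre-dose sample is drawn, and the Day 7/Day 14 trough model cannot date steady state

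*Protocol*

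**What the plan says.** Section 9.9.1.3 describes a power model for exposure against dose and a linear regression of t1/2 and CL/F on dose. It then says the same analysis will be done for Cmax, AUCtau, t1/2 and CL/F "for Part 2 of the study on Days 1, 7 and 14".

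Table 9.7.2, footnote 9, fixes the Part 2 PK draws. After the Day 1 series it reads "6h and 12h post-dose; Day 2, 3 and 7 prior to dosing = 0h; Day 14 prior to dosing = 0h", followed by the post-dose times for Day 14 out to 24 h. Footnote 10 has a further Day 7 blood draw, "Day 7 at 2h post-dose and Day 14 prior to dosing = 0h and then at 30 min post-dose", but that one is for mRNA and flow cytometry.

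Two related analyses stand beside this in section 9.9.1.3:

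- **Accumulation** uses pre-dose levels from Day 2 to Day 14: "The ratio of trough concentrations on each consecutive day will be presented", with a 90% confidence interval.
- **Steady state** uses a mixed-effects ANOVA of the Day 7 and Day 14 troughs, "in order to establish whether and when steady state has been attained for each dose level". The one contrast reported is the Day 14/Day 7 ratio.

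Section 9.9.1.1 defines CL/F as "Plasma clearance, calculated as Dose" divided by AUC0-inf, without distinguishing single from repeated dosing.

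**The concern.** The analysis text names a day for which the schedule supplies no profile. A SAP can choose methods, but it cannot recover samples that were never drawn, so it would have to depart from the protocol on Day 7.

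The steady-state paragraph has a milder fault. The model that is meant to say when steady state is reached leaves out the two early troughs (Days 2 and 3) that carry that information, although both are drawn. The accumulation wording implies daily troughs that do not exist. On Day 14, AUC0-inf includes drug left over from earlier doses, so the generic CL/F definition is biased low there.

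What is at stake is the multiple-dose PK objective in section 8.2, which is secondary. The primary safety objective is untouched.

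**Working it through.** **1. PK draws per subject in Part 2 (Table 9.7.2, footnote 9)**

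| Day | Draws | Count |
|---|---|---|
| 1 | 0, 15, 30, 45 min; 1, 2, 3, 4, 5, 6, 12 h | 11 |
| 2, 3, 7 | pre-dose only | 1 each |
| 14 | the same 11 times plus 24 h | 12 |

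Total: 11 + 3 + 12 = 26. The Day 2 pre-dose draw serves as the 24 h point for Day 1. Post-dose PK draws on Day 7: 0.

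**2. What Day 7 can support.** Section 9.9.1.3 derives the parameters from each subject's concentration-time data. A single trough gives no post-dose maximum, no area over the dosing interval, no terminal slope and hence no t1/2, and no CL/F. Planned cells: 4 parameters × 3 days = 12. Cells without post-dose data: 4.

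**3. Trough pairs for accumulation.** From Day 2 to Day 14 there are 13 days, of which 4 have a trough (2, 3, 7, 14). There are 12 calendar-consecutive pairs, and only Day 3/Day 2 has both values. Consecutive sampled days give 3 ratios.

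**4. Where the approach to steady state falls.** Section 9.6.7 gives a half-life of about 6 h in animals and says "little or no accumulation after 14-day dosing and is excreted in the faeces". No human half-life is given. I take 6 h, with 3 to 12 h (half to double) as an assumed range and 24 and 48 h as a stress check. Assuming one compartment, bolus-like input, dosing every 24 h and no missed doses, the trough after n doses, as a share of steady state, is

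1 − 2^(−24n / t1/2), with n = 1, 2, 6, 13 for Days 2, 3, 7, 14.

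| t1/2 | Day 2 | Day 3 | Day 7 | Day 3/Day 2 | Day 14/Day 7 |
|---|---|---|---|---|---|
| 3 h | 99.6% | >99.9% | >99.9% | 1.004 | 1.000 |
| 6 h | 93.8% | 99.6% | >99.9% | 1.063 | 1.000 |
| 12 h | 75.0% | 93.8% | 99.98% | 1.250 | 1.000 |
| 24 h | 50.0% | 75.0% | 98.4% | 1.500 | 1.016 |
| 48 h | 29.3% | 50.0% | 87.5% | 1.707 | 1.130 |

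Up to about 24 h, the rise is essentially over before the first day the ANOVA uses. A Day 14/Day 7 ratio near 1 then supports a statement that steady state was reached by Day 7. It cannot say how much earlier.

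**5. Precision.** Each dose level has 5 TD139 subjects. If a cohort is expanded (section 9.1: "4 further subjects would be dosed in Cohort 1 with 3mg (3 TD139 and 1 placebo"), it has 8. For a paired ratio, the log-scale 90% half-width is t(0.95, n−1) × s × √(2/n), with s = √ln(1 + CV²). With an assumed within-subject CV of 20%, s = 0.198. For n = 5 the half-width is 2.132 × 0.198 × 0.632 = 0.267, so the interval around a ratio of 1 is 0.77 to 1.31. At a CV of 50% it is 0.53 to 1.89. For n = 8 at 20% it is 0.83 to 1.21. A four-day model with 5 subjects has 4 × 3 = 12 residual degrees of freedom: 1.782 × 0.198 × 0.632 = 0.223, giving 0.80 to 1.25.

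**6. Day 14 CL/F.** At steady state AUC0-inf / AUCtau = 1 / (1 − 2^(−24 / t1/2)): 1.004 at 3 h, 1.067 at 6 h, 1.333 at 12 h. Dose/AUC0-inf is therefore below Dose/AUCtau by 0.4%, 6.25% and 25%.

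**The case against.** Four points can be made for the plan.

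- **PK sampling times may be changed after an interim review** (sections 9.1 and 9.2.2). That option is discretionary and comes after Cohort 1 has been dosed. It puts no Day 7 profile in the current schedule and could not supply one for that cohort.
- **The early troughs are reported anyway**, in the accumulation ratios with 90% intervals. This is true and limits the harm: the information is partly in the plan, though not in the analysis said to establish timing.
- **Adding Days 2 and 3 would not date steady state precisely.** This also stands. At 6 h the expected Day 3/Day 2 rise is about 6%, while the 90% interval with 5 subjects is about 0.80 to 1.25 even at an assumed CV of 20%. Deleting the claim about timing is therefore as good a remedy as enlarging the model.
- **The kinetic figures rest on an animal half-life and a simple model for an inhaled drug.** At 48 h the Day 7 trough would be 87.5% of steady state. That is fair, so the statement that the rise precedes Day 7 is conditional. The Day 7 contradiction needs none of it.

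The consecutive-day phrase can be read as consecutive sampled days, so that point is editorial. The CL/F definition suits Part 1 and Day 1, and its bias on Day 14 is small if the half-life is near 6 h.

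**Conclusion.** The concern holds. The Day 7 parameter analysis cannot be carried out on the schedule as written. This follows from two places in the same document and rests on no assumption. One of the three planned analysis days is empty.

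The steady-state claim is too strong: one Day 14/Day 7 contrast can support attainment by Day 7 but cannot show when. How little it can show depends on the assumed half-life and one-compartment model, but having only one contrast does not. The accumulation wording and the Day 14 CL/F definition are lesser faults. The size of the CL/F bias (0.4% to 25%) depends on the assumed 3 to 12 h range.

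This should be fixed, at modest priority, because only secondary PK results are affected.

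**What to change.** 1. Reconcile section 9.9.1.3 with Table 9.7.2, footnote 9. The cheapest way is to limit the Part 2 analysis of Cmax, AUCtau, t1/2 and CL/F to Days 1 and 14.
2. Fit the steady-state mixed model to the Day 2, 3, 7 and 14 troughs, which gives 3 successive contrasts instead of 1, and acknowledge its imprecision with 5 (or 8) TD139 subjects per dose level. Alternatively, drop the claim about when and keep only whether.
3. In the accumulation paragraph, refer to consecutive sampled days (2, 3, 7, 14).
4. State that Day 14 CL/F is Dose/AUCtau, or note the carry-over in Dose/AUC0-inf.

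A Day 14/Day 1 ratio of AUCtau and Cmax would be a useful optional addition, since both profiles are drawn.

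The cost is wording only, with no new samples. If the authors did intend a Day 7 profile, the sampling schedule itself must be amended before the subjects concerned reach Day 7, because those samples cannot be recovered later.
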